1.0 Introduction and Background

Lung cancer (LC) is the third most common cancer in both men and women and the leading cause of cancer death.¹ Non-small cell (NSC) lung cancer includes three main subtypes, squamous cell carcinoma (25%), adenocarcinoma (40%), and large cell carcinoma (10%).² Only approximately 15% of lung cancer cases are diagnosed at the local stage.¹

Major oncogenic drivers in non-small cell lung cancer include mutations in EGFR, translocations in Alk, and translocations in ROS-1. National Comprehensive Cancer Network (NCCN) guidelines also have supported the use of medications targeting BRAF, Met, HER-2, and RET. Investigators have reported emergence of mutations in a secondary oncogenic drivers at the time of progression on tyrosine kinase inhibitor therapy for patients whose tumors harbor primary activating mutations in one of the major three (EGFR, Alk, or ROS-1) drivers.

The plan of care for patients whose cancer progresses on treatment with one of the major 3 driver mutations may include sequencing of the primary driver gene for emergence of an additional mutation in that gene. Immunotherapy may also benefit some patients with acquired resistance, but the role of these medications is not well defined. High PD-L1 expression and response to immunotherapy has been reported in patients with oncogenic drivers who smoke cigarettes.

The use of expanded genetic testing in this situation to identify mutations in genes other than the primary driver gene (secondary mutations) is attractive for exploring all available treatment options. The outcomes of patients who undergo testing and have mutations in a secondary gene have not been prospectively studied. Available options include alternative agent targeting the original driver mutation, changing treatment to target the mutation in the secondary gene, combination therapy targeting both, or other treatments such as chemotherapy, immunotherapy, or clinical trials.

The goal of this protocol is to evaluate the efficacy of treatment tailored to the immunogenic and mutation profiles of patients on EGFR, MET, BRAF, V600E, RET, HER2, Alk, or ROS-1 inhibitors at the time of progression. This pilot study will compare the clinical outcomes for treatment of resistance targeting the primary mutations, secondary mutations, or immunotherapy.

2.0 Objectives

2.1 Primary Objective(s)

- 2.1.1 To estimate the objective response rate among patients with high PD-L1 expressing cancers after failure of targeted therapy.

2.2 Secondary Objective(s)

- 2.2.1 To compare the overall survival for patients receiving treatment targeting primary mutations, secondary mutations, or immunotherapy at the time of progression on tyrosine kinase inhibitor therapy

Phase II Pilot Study Evaluating Strategies to Overcome Resistance at the Time of Progression
for Patients with Non-Small Cell Lung Cancers Harboring Major Oncogenic Drivers
Wake Forest Baptist Comprehensive Cancer Center (CCCFWU)
CCCFWU 62716
ClinicalTrials.gov: NCT02949843

- 2.2.2 To assess the incidence of secondary mutations in this population according to smoking status.
- 2.2.3 To evaluate the response rates of patients treated using these different approaches.
- 2.2.4 To correlate outcomes with specific secondary genetic changes.

3.0 Patient Selection

3.1 Inclusion Criteria

- 3.1.1 Patients must have histologically or cytologically confirmed incurable non-small cell lung cancer that harbors an activating mutation in EGFR, MET, BRAF, V600E, RET, HER2, translocation in Alk, or translocation in ROS-1.
- 3.1.2 Patients must be receiving treatment or planning to start treatment with a tyrosine kinase inhibitor targeting the activated gene.
- 3.1.3 Patients may not be receiving the treatment targeting the activated gene as part of a clinical treatment trial other than the Precision Oncology Trial.
- 3.1.4 ECOG performance status of 0-3.
- 3.1.5 Patients must have normal organ function as defined below:
 - AST(SGOT)/ALT(SGPT) $\leq 2.5 \times$ institutional upper limit of normal
- 3.1.6 These agents may be teratogenic; therefore, women of child-bearing potential and men must agree to use adequate contraception (hormonal or barrier method of birth control) prior to study entry and for the duration of study participation. Should a woman become pregnant or suspect she is pregnant while participating in this study, she should inform her treating physician immediately.
- 3.1.7 Ability to understand and the willingness to sign an IRB-approved informed consent document

3.2 Exclusion Criteria

- 3.2.1 Emergent need for palliative radiation.
- 3.2.2 Patients may not be receiving any other investigational agents for the treatment of non-small cell lung cancer.
- 3.2.3 Uncontrolled intercurrent illness including, but not limited to ongoing or active infection, symptomatic congestive heart failure, unstable angina pectoris,

Phase II Pilot Study Evaluating Strategies to Overcome Resistance at the Time of Progression
for Patients with Non-Small Cell Lung Cancers Harboring Major Oncogenic Drivers
Wake Forest Baptist Comprehensive Cancer Center (CCCWFU)
CCCWFU 62716
ClinicalTrials.gov: NCT02949843

cardiac arrhythmia, or psychiatric illness/social situations that would limit compliance with study requirements.

3.2.4 Pregnant women are excluded from this study because of the potential for teratogenic or abortifacient effects with chemotherapy. Because there is an unknown but potential risk for adverse events in nursing infants secondary to treatment of the mother with chemotherapy, breastfeeding should be discontinued.

3.3 Inclusion of Women and Minorities

Men and women of all races and ethnicities who meet the above-described eligibility criteria are eligible to participate in this study.

The study consent form will also be provided in Spanish for Spanish-speaking participants. Based on WFBCCC population estimates, we expect approximately 44% of participants to be women. Translating this to our sample size estimate of up to 75, we plan to enroll at least 33 women. We plan to enroll at least 11% Black or African Americans (N=8). Because of the low incidence of lung cancer in our catchment area in the Hispanic/Latino (.8% or possibly an N=1), Asian, and American Indian/Alaska native populations we would not expect to obtain individuals from these populations in this particular study. Should we not meet or exceed these estimates, the PI will engage the Cancer Center Health Equity Advisory Group to discuss strategies to enhance recruitment in these target populations.

4.0 Registration Procedures

All patients entered on any WFBCCC trial, whether treatment, companion, or cancer control trial, **must** be registered with the WFBCCC Protocol Registrar or entered into ORIS Screening Log within 24 hours of Informed Consent. Patients **must** be registered prior to the initiation of treatment.

You must perform the following steps in order to ensure prompt registration of your patient:

1. Complete the Eligibility Checklist (Appendix A)
2. Complete the Protocol Registration Form (Appendix B)
3. Alert the Cancer Center registrar by phone, *and then* send the signed Informed Consent Form, Eligibility Checklist and Protocol Registration Form to the registrar, either by fax or e-mail.

Contact Information:

Protocol Registrar [contact]

Protocol Registrar [contact]

Protocol Registrar E-MAIL ([contact])

*Protocol Registration is open from 8:30 AM - 4:00 PM, Monday-Friday.

4. Fax/e-mail ALL eligibility source documents with registration. Patients **will not** be registered without all required supporting documents.

Phase II Pilot Study Evaluating Strategies to Overcome Resistance at the Time of Progression
for Patients with Non-Small Cell Lung Cancers Harboring Major Oncogenic Drivers
Wake Forest Baptist Comprehensive Cancer Center (CCCFWU)
CCCFWU 62716
ClinicalTrials.gov: NCT02949843

Note: If labs were performed at an outside institution, provide a printout of the results.
Ensure that the most recent lab values are sent.

To complete the registration process, the Registrar will:

- assign a patient study number
- register the patient on the study

5.0 Study Outcomes and Study Measures

5.1 Primary Outcome

5.1.1 The primary outcome measure is the objective response rate among patients with high PD-L1 expressing cancers after failure of targeted therapy

5.2 Secondary Outcomes

5.2.1 Overall survival (OS) of three patient cohorts (immunotherapy sensitive, primary targetable mutation, and secondary targetable mutation) is the first secondary outcome.

5.2.2 Objective response rates for the other patient cohorts (patients without high PD-L1 expressing cancers) and the combined population to historical controls receiving second or third line targeted agents.

5.2.2 Toxicities which will be measured using CTCAE version 4.0

5.2.3 Incidence of mutations in secondary genes

5.2.4 Rate of tobacco use and mutation burden by patient group based on PD-L1 expression (yes/no) at the time of progression.

6.0 Treatment Plan

6.1 Study-Related Interventions

	Pre-Study ^a	At Each Treatment	After First-Progression	Follow-up
Informed consent	X			
Demographics	X			
Medical history	X			
Concurrent meds	X			
Physical exam	X		X	X
Vital signs	X		X	X
Height, Weight, M ²	X			
Performance Status	X		X	X
Tumor measurements			X	X ^d
CBC w/diff, platelets	X	X	X	X
Serum chemistry ^b	X	X	X	X
B-HCG ^c	X			
Adverse event evaluation		X	X	X
Tobacco Use Assessment	X		X	
Research blood (plasma)	X		X	
Tumor Biopsy			X	

a: Pre-study requirements listed in table must be completed **within** 14 days prior to registration.
 b: Alkaline phosphatase, total bilirubin, BUN, calcium, creatinine, SGOT[AST], SGPT[ALT]
 c: Serum pregnancy test (women of childbearing potential).
 d: After the patient receives first dose of study drug they should be followed for progression on the following time line: for patients receiving nivolumab, imaging should be performed every 8 weeks +/- 3 days for the first two imaging studies. For patients receiving pembrolizumab, imaging should be performed every 9 weeks +/- 3 days for the first two imaging studies. After the first two imaging studies, additional follow-up imaging interval will be at the investigator's discretion. For patients receiving other treatments, all follow-up imaging intervals will be at the investigator's discretion.

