6.2 Treatment Administration

Patients currently receiving or about to start treatment with an oral tyrosine kinase inhibitor for one of the major oncogenic drivers (EGFR, MET, BRAF, V600E, RET, HER2, Alk, or ROS-1) will be eligible. At the time of registration, blood samples will be obtained for plasma and other biomarker analyses (Appendix J), tobacco use (Appendix D) and performance status (Appendix K) will be determined. Treatment with an agent targeting the primary oncogenic driver will be continued until progression. If a new agent is approved for treatment of the primary driver, patients may be changed prior to progression at the investigator's discretion.

At the time of progression, patients will undergo repeat biopsy to determine PD-L1 staining and large scale genetic testing. Foundation Medicine testing is preferred but patients may have testing performed by other platforms including Guardant 360. Other platforms may be used after discussion with the principal investigator. Research plasma and tissue will be collected (Appendix J). Patients will also complete a detailed tobacco use questionnaire at the time of progression (Appendix E). Further, Performance Status will be determined (Appendix K). While awaiting results of testing, patients may continue the current treatment targeting the primary oncogenic driver.

Phase II Pilot Study Evaluating Strategies to Overcome Resistance at the Time of Progression
for Patients with Non-Small Cell Lung Cancers Harboring Major Oncogenic Drivers
Wake Forest Baptist Comprehensive Cancer Center (CCCFWU)
CCCFWU 62716
ClinicalTrials.gov: NCT02949843

If the PD-L1 testing result is $\geq 50\%$, patients will receive immunotherapy with either nivolumab or pembrolizumab as subsequent treatment. If patients have PD-L1 testing result that is $< 50\%$, the large scale testing will be used to determine the presence of absence of a secondary driver. For the purposes of the study, a secondary oncogenic driver will be considered an activating genetic change in a gene other than the primary oncogenic driver gene that has an effective treatment. These would include EGFR, Alk, ROS-1, MET, BRAF V600E, RET, and HER2. Classification of a genetic alteration as a secondary driver will be determined by the investigator.

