For patients without secondary oncogenic drivers, treatment will be categorized as subsequent line of treatment, targeting the primary oncogenic driver, or other treatment. For patients with secondary oncogenic drivers, treatment will be categorized as treatment targeting secondary oncogenic driver, subsequent line of treatment targeting the primary oncogenic driver or other treatment. Targeted treatments may include those treatments listed on NCCN Guidelines. Initial medication dose and dose modifications should be implemented according to standard of care guidelines.

Treatment will be administered on an inpatient or outpatient basis. Reported adverse events and potential risks are described in Section 9.0. No investigational or commercial agents or therapies other than those described below may be administered with the intent to treat the patient's malignancy.

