6.4 Duration of Therapy

The duration of the research treatment is through the first follow-up CT scan after the addition of second-line treatment with nivolumab or pembrolizumab. Treatment may continue beyond this point at the investigator's discretion. In the absence of treatment delays due to adverse events, treatment may continue until one of the following criteria applies:

- Disease progression,
- Intercurrent illness that prevents further administration of treatment,
- Unacceptable adverse event(s), specifically if Grade 3 or 4 neurotoxicity is observed
- Patient decides to withdraw from the study, or
- General or specific changes in the patient's condition render the patient unacceptable for further treatment in the judgment of the investigator.

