12.0 Statistical Considerations

12.1 Introduction

By design patients will be enrolled in this study prior to the determination of their PD-L1 status. In addition, among patients with low PD-L1 expression (<50%) it cannot be determined prospectively how many patients after disease progression will have a secondary oncogenic driver identified. Thus, patients upon enrollment may enter one of three arms to be determined at a later time – 1) PD-L1 expression $\geq 50\%$, 2) PD-L1 expression <50% with secondary oncogenic driver identified and 3) PD-L1 expression <50% without secondary oncogenic driver identified. It is anticipated that less than 50% of patients will have PD-L1 expression $\geq 50\%$, thus this arm – which is the focus of the primary objective – will take longer to fill. In order to manage the overall sample size expectations of this study, the design will allow enrollment to continue until 15 patients are enrolled in the PD-L1 expression $\geq 50\%$ arm (sample size needed based on Simon's two stage design described below). Each of the other two arms will allow enrollment until a minimum of 15 and maximum of 30 patients are enrolled into each arm. If the maximum (n=30) is reached in either of the PD-L1 expression < 50% arms, then new patients eligible for those arms will not be included in the follow-up assessments.

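### Section 6.1 requires one pregnancy test, at registration, and no repeat before the first nivolumab or pembrolizumab dose, which follows a TKI course with no stated maximum length

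*Combined protocol and SAP*

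**What the plan says.** The table in section 6.1 has four columns: Pre-Study, At Each Treatment, After First-Progression and Follow-up. B-HCG is marked in the first only. Footnote c describes it as "Serum pregnancy test (women of childbearing potential"), and footnote a ties the Pre-Study column to the 14 days before registration.

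Registration comes before or during TKI therapy (3.1.2). Section 6.2 then states: "Treatment with an agent targeting the primary oncogenic driver will be continued until progression". At progression the patient has a repeat biopsy for PD-L1 and genetic testing, and may stay on the TKI while results are awaited. If PD-L1 is at least 50%, "patients will receive immunotherapy with either nivolumab or pembrolizumab as subsequent treatment". Section 6.4 defines the study's own treatment period by that step: the "research treatment is through the first follow-up CT scan after the addition of second-line treatment with nivolumab or pembrolizumab".

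The other provisions on pregnancy are in section 3. Under 3.1.6, "women of child-bearing potential and men must agree to use adequate contraception" before entry and throughout participation, and a woman who is or suspects she is pregnant is told that "she should inform her treating physician immediately". Section 3.2.4 excludes pregnant women, and the Appendix A checklist records that exclusion at registration.

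**The concern.** A pre-study pregnancy test is most useful when it sits close to the first dose of the treatment of interest. Here it is tied to registration, and the PD-1 drug comes later, after the TKI course and the wait for results. For a woman who registers at the start of her TKI, the gap is the whole of that course. The registration result then says little about her status when immunotherapy begins.

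The protocol regards fetal exposure as serious enough to require contraception, to exclude pregnant women and to require a serum test at entry. Yet a pregnancy that arises during the TKI period and is not suspected would meet no required test before PD-1 exposure. Such a pregnancy would already have been exposed to the TKI. A repeat test would therefore limit further exposure, to a different class of drug, and would not prevent all exposure.

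**Working it through.** The plan gives no figure to reproduce here. The check is a reading of the schedule, followed by simple counts.

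**1. Required tests.** In the 6.1 table, B-HCG is marked at one of four time points. Physical exam, vital signs, performance status, CBC and chemistry are marked again under After First-Progression, and B-HCG is not. Because neighbouring rows carry marks in the later columns, the blanks in the B-HCG row do not look like a fault in reading the table.

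**2. Any requirement elsewhere.** I looked at each place where one might be found:
- 3.1.6: contraception and self-report, no test.
- 3.2.4 and Appendix A: an exclusion confirmed at registration, no later re-check.
- 6.2: "Initial medication dose and dose modifications should be implemented according to standard of care guidelines". This covers dose, not pregnancy testing.
- 6.4: the investigator may stop treatment if the patient's condition changes, no test.
- 6.7, 6.8, 9.2 and 9.3 (the PD-1 drugs): no test.
- 9.0: refers to package inserts for drugs directed at secondary mutations, which does not cover nivolumab or pembrolizumab.

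**3. Length of the gap.** Time from test to first PD-1 dose = up to 14 days before registration + time from registration to progression + wait for biopsy and PD-L1 results. The protocol limits only the first term.

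**4. Number of women in the PD-1 arm.** Section 3.3 expects about 44% women. Section 12.1 sets the arm size: "the design will allow enrollment to continue until 15 patients are enrolled in the PD-L1 expression" ≥50% arm. Assume the 44% applies within this arm.
- Expected women: 0.44 × 15 = 6.6.
- If the number is binomial (15, 0.44): SD = √(15 × 0.44 × 0.56) = 1.92; P(3 to 10) = 0.97; P(more than 7) = 0.32. So 6.6 is an expectation and not a ceiling.
- If the trial stops after the first 8 patients (12.2): 0.44 × 8 = 3.5.

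**5. Women of childbearing potential.** The documents do not give this share. Under assumed values, for the full arm of 15:

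| Assumed share | Expected women to retest |
|---|---|
| 10% | 6.6 × 0.10 = 0.7 |
| 30% | 6.6 × 0.30 = 2.0 |
| 100% (formal bound) | 6.6 |

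**6. If every arm were tested at progression.** The two PD-L1 <50% arms together hold 30 to 60 patients, so 0.44 × 30 = 13.2 to 0.44 × 60 = 26.4 women. Adding 6.6 gives 19.8 (N = 45) to 33 (N = 75), before restricting to childbearing potential.

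These are counts of women who would be tested. The documents give no basis for the probability of an unsuspected pregnancy, so harm avoided cannot be estimated.

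**The case against.** The strongest reply is that the risk is already managed. Contraception is required for the whole of participation, a suspected pregnancy must be reported at once, there is a physical exam after first progression, and the investigator may stop treatment. What remains is a pregnancy that occurs despite contraception, is unsuspected by the patient and is missed at that visit, in perhaps one or two women at risk across the trial. This stands as an argument about size, and it is why the point is minor. It does not remove the gap. The same contraception and self-report rules applied at entry, and the protocol still required a test there.

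A second reply is that sites would test under usual care before a PD-1 drug. They may. A reader might infer from the table that women will start immunotherapy untested. The documents do not support that: they show only that the protocol does not require a repeat. Equally, the standard-of-care sentence in 6.2 is about dosing and cannot be read as requiring one.

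A third reply concerns scope. Section 3.1.6 speaks of the agents in general, and 3.2.4 gives its reason in terms of chemotherapy. Neither singles out PD-1 drugs. This stands. The case for starting with the PD-1 dose is that 6.2 assigns that treatment and 6.4 defines the research treatment by it, whereas post-progression treatment in the other two arms is only categorized. That is a reason for priority, and it does not show that other new agents are safer.

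Finally, the gap need not be long. A patient may register late in her TKI course and progress soon after. The accurate statement is that no maximum is given, because the period ends at progression plus the wait for results.

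**Conclusion.** The point holds as a minor patient-safety improvement. The required pregnancy test is timed to registration, and none is required before the first nivolumab or pembrolizumab dose. That rests directly on the 6.1 table and on the absence of a requirement in any other section supplied.

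Few women are affected: a subset of about 6.6 expected in the PD-1 arm, assuming that the protocol's 44% applies there and that the arm fills to 15. The share of childbearing potential is unknown, and the 0.7 to 6.6 range rests on assumed values.

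A reader might also infer that the gap undermines the trial's results, because the primary objective concerns this arm. It does not. The Simon two-stage design, the arm sizes and the analyses are unaffected, and nothing in the documents suggests that a pregnant woman has been or would knowingly be treated.

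**What to change.** Extend footnote c in section 6.1 to add: *repeat in women of childbearing potential within 14 days before the first nivolumab or pembrolizumab dose, with a negative result available before dosing.* Cross-reference it in the B-HCG row itself, for example beside the row label. A mark under At Each Treatment is best avoided: the protocol does not define that column, and it could be read as covering the TKI period. An unqualified mark under After First-Progression would also be imprecise, since the biopsy that determines PD-L1 status sits in the same column and the arm is not yet known.

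The assay can use any blood draw in the 14-day window, such as the CBC and chemistry draw after first progression if it falls within it. If that draw is used before the PD-L1 result is back, some women who then enter the other arms will be tested too.

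The cost is one extra assay per eligible woman and, if blood is drawn on the dosing day, a possible short wait for the result. The sponsor may choose to apply the same rule to new agents started in the PD-L1 <50% arms, since 3.1.6 does not single out PD-1 drugs. With all arms covered, the pool would be at most 19.8 to 33 expected women before restriction to childbearing potential.
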